**Date of document: (Version 3 13/04/2018)**

### Clinical hypothesis

The primary hypothesis is that increased mean radiation dose to the teeth and to the 'spared' parotid gland is associated with an increase in the mean number of carious teeth and in the proportion with periodontal disease 2 years post-radiotherapy.

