### **Study design: Prospective cohort study.**

- Pre-radiotherapy assessment at baseline and patients rendered dentally fit (i.e. free of dental disease).
- Post-radiotherapy follow-up assessments at 6 months, 12 months, and 24 months.

**Selection criteria:** Adult dentate patients (i.e. patients with natural teeth) diagnosed with a primary or secondary malignant tumour of the oral cavity, nasal cavity, sinuses, salivary glands, pharynx, or larynx\* requiring radiation treatment within Northern Ireland. \*International Classification of Diseases (ICD-10) codes C00.0-C14.8 and C30.0-32.9.

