### Clinical assessment

**-Dental caries:** The presence or absence of dental caries on each tooth will be determined using the World Health Organization's criteria and coding system, and ICDAS, and recorded in a modified version of the Oral Health Assessment Form for Adults, 2013. All surfaces of the crown and root of each tooth will be assessed by: visualisation using a mouth mirror, dental probe, adequate lighting, and compressed air from a 3-in-1 tip.

Presence or absence of dental caries on each surface will be recorded as follows (Figures 1 and 2):

Code		Condition/status	
Primary teeth	Permanent teeth	Crown	Root
A	0	0	Sound
B	1	1	Caries
C	2	2	Filled, with caries
D	3	3	Filled, no caries
E	4	—	Missing due to caries
—	5	—	Missing for any other reason
F	6	—	Fissure sealant
G	7	7	Fixed dental prosthesis abutment, special crown or veneer/implant
—	8	8	Unerupted tooth (crown)/unexposed root
—	9	9	Not recorded

Figure 1: WHO criteria and coding system

[figure not shown]

Figure 2: ICDAS coronal caries decision tree

**-Periodontal disease:** A six-point periodontal charting will be performed for all patients. Clinical attachment loss and probing pocket depths will be measured using a Williams Periodontal Probe and recorded for six sites on each tooth using the Oral Health Assessment Form. The 'Centers for Disease Control and Prevention (CDC)', in partnership with the 'American Academy of Periodontology (AAP)' workgroup definition of periodontitis will be used to identify those with active periodontal disease: 2 or more interproximal sites with attachment loss  $\geq 3$  mm, and 2 or more interproximal sites with pocket depths  $\geq 4$  mm (not on same tooth) or one site with pocket depth  $\geq 5$  mm.

**-Stimulated salivary flow rate** using paraffin pellets. Patients will chew an unflavoured paraffin pellet for 5 minutes whilst expectorating into a pre-weighed disposable specimen pot. This will be undertaken in one of the private units in the Prosthetics Department of the School of Dentistry, Belfast. Following collection, the specimen pot will be transported to the Institute of Pathology, Royal Victoria Hospital, Belfast. The mass of collected saliva will be determined using a calibrated precision weighing balance. After the calculation of salivary flow rate, each patient's saliva sample will be disposed of as clinical waste and destroyed by incineration in line with the Human Tissue Act 2004.

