### Denture hygiene instruction

- Don't wear dentures during the course of radiotherapy if possible
- Rinse dentures after every meal in cold running water
- Clean dentures at least once daily with a toothbrush and 5,000 ppm Duraphat fluoride toothpaste
- Soak in Milton's (1 in 80 dilution) overnight if the denture is made of plastic only
- Alternatively, soak in Corsodyl (chlorhexidine gluconate) 0.2% overnight if the denture has metal components

A dental treatment plan will be formulated for each patient to ensure adequate dental fitness prior to radiotherapy. Consultants in Restorative Dentistry, will oversee patients' treatment plans. Dental treatment required pre-radiotherapy (e.g. restorations and extractions) will be co-ordinated by the School of Dentistry in line with current practice, including the possibility of routine treatment within the primary care setting (i.e. completed by the patient's general dental practitioner).

To facilitate the micro-costings study, all patients will be asked to retain details of any treatment costs that they incurred from their general dental practice. Patients will be asked to provide this cost information at follow-up appointments (for example, with the production of invoices). Information on the cost of dental treatment incurred will be recorded on each patient's anonymised questionnaire booklet completed at the subsequent follow-up appointment.

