#### **1. Extractions**

The following table is intended to guide the decision-making process for pre-radiotherapy dental extractions in line with current practice. The decision to undertake extractions should be taken after careful consideration of individual tooth prognosis, tooth abutment potential, and the patient's medical history (see also 'SPECIAL CASES' below).

	Molars	Premolars	Anteriors
Apical disease	YES	YES when both marginal ridges lost	YES if post-crown
Furcation disease	YES	YES	N/A
Grade II mobile or worse	YES	YES	YES
Loss of >50% marginal bone loss	YES	YES	YES
Crown with secondary caries	YES	YES if post-crown	YES if post-crown
Crown with subgingival margins	YES	YES	NO
Caries or toothwear with suspected pulpal involvement	YES	YES when both marginal ridges lost	NO
Previous RCT/non-vital tooth	YES	YES when both marginal ridges lost	NO
Caries/tooth margin >1mm subgingival	YES	YES	YES
Root caries >1 surface	YES	YES	YES
Root perforation/ resorption/ fracture/ retained instrument	YES	YES	YES
Periodontal pocket >5mm	YES	YES	YES

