## **Statistical analysis**

Primary outcome measures to be analysed include: (1) the number of carious teeth and (2) the presence of periodontal disease.

(1) Initial comparisons between the radiation dose to the 'spared' parotid gland and the number of carious teeth will be performed using independent t-tests (categorising radiation dose as <20Gy and >20Gy) and ANOVA (categorising radiation dose as <20Gy, 20-30Gy, 30-40Gy, and >40Gy) as appropriate. Adjusted analysis will be performed using multiple linear regression, with the number of carious teeth as the outcome variable, radiation dose to the 'spared' parotid gland as an explanatory variable

(categorised as above) along with potential confounding variables: dental radiation dose, oral hygiene practice, diet, and mouth opening. Without categorising radiation dose, a separate analysis will be conducted using linear regression with the number of carious teeth as the outcome variable and radiation dose to the 'spared' parotid gland (Gy) as the explanatory variable to give the increase in the number of carious teeth per 10 unit increase in Gray. If the number of carious teeth is not normally distributed transformations will be used prior to analysis or equivalent non-parametric techniques will be used.

(2) Initial comparisons of the association between radiation dose to the 'spared' parotid gland (categorised as above) and the presence of periodontal disease (Yes/No) will be performed using chi-square tests. Adjusted analysis will be performed using logistic regression with presence of periodontal disease as the outcome variable, radiation dose to the 'spared' parotid gland as the explanatory variable and dental radiation dose, oral hygiene practice, diet, smoking, medical history, and mouth opening as potential confounders.

Similar analyses will be undertaken to determine the effects of dental radiation dose and tumour location on the number of carious teeth and the presence of periodontal disease in post-radiotherapy head and neck cancer patients.

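### The adjusted model for the primary periodontal outcome omits baseline periodontal status, so some disease present before radiotherapy may be counted as outcome

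*Combined protocol and SAP*

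**What the plan says.** The Clinical hypothesis section states the periodontal part of the primary hypothesis as a difference "in the proportion with periodontal disease 2 years post-radiotherapy". Part (2) of Statistical analysis makes the outcome a yes/no variable. It begins with chi-square tests by parotid dose category and continues: "Adjusted analysis will be performed using logistic regression with presence of periodontal disease as the outcome variable". The listed potential confounders are dose to the teeth, oral hygiene, diet, smoking, medical history and mouth opening. Baseline periodontal status is not listed. The parallel analyses for dental dose and tumour location follow the same pattern.

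The baseline value exists. Under Clinical assessment, "A six-point periodontal charting will be performed for all patients", and the Spreadsheets section keeps one clinical data file per assessment visit. The same charting is repeated at 6, 12 and 24 months.

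The Study design section gives the intended starting state: "Pre-radiotherapy assessment at baseline and patients rendered dentally fit (i.e. free of dental disease". Before radiotherapy this is pursued by extraction, under a table that "is intended to guide the decision-making process for pre-radiotherapy dental extractions", and by non-surgical periodontal treatment. Treatment is co-ordinated by the dental school, "including the possibility of routine treatment within the primary care setting".

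**The concern.** A prevalent outcome mixes two kinds of patient: those who develop disease after radiotherapy and those who already had it. The hypothesis concerns what radiation dose does, so only the first kind, together with true recurrence, bears on it. Neither the exclusion criteria nor the outcome definition removes baseline cases.

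Radiotherapy is prescribed and planned clinically, so dose groups may differ in dental health before treatment. If they differ in periodontal disease beyond what the six listed confounders explain, and enough of that disease is still present at 24 months, the model will credit or debit dose with something that came before it. The error can run either way. One of the two primary outcomes is affected, and the variable that would address it is already collected.

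**Working it through.** **1. Can a baseline case survive the preparation?** Compare the thresholds.

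- Case definition (Clinical assessment): attachment loss of 3 mm or more at two or more interproximal sites, plus either two interproximal sites on different teeth with pockets of 4 mm or more, or one site of 5 mm or more.
- Periodontal rows of the extraction guide: furcation disease, grade II mobility or worse, "Loss of >50% marginal bone loss" and "Periodontal pocket >5mm".

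A patient with pockets of 4 to 5 mm and the required attachment loss, and nothing else in the table, is a case but meets no extraction row. That patient has non-surgical treatment, for which no periodontal end-point is given. No re-charting is described until 6 months after radiotherapy. Freedom from disease is therefore an aim that the plan does not verify against its own case definition.

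**2. The plan's own figures.** The sample size rests on the caries outcome: 150/(1 - 0.30) = 214.3, rounded up to 215, which reproduces. No figure is given for the periodontal outcome. I take from that section 150 evaluable patients and the 80%/20% split: 0.20 x 150 = 30 under 20 Gy and 120 over.

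**3. Direct arithmetic, all rates assumed.** Follow-up prevalence = b x p + (1 - b) x n, where b is baseline prevalence, p is persistence in baseline cases and n is the rate of new cases. Take n = 20%, b = 30% (low dose) v 50% (high dose), and no dose effect.

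- p = 80%: 0.30 x 0.80 + 0.70 x 0.20 = 38% v 0.50 x 0.80 + 0.50 x 0.20 = 50%. Odds ratio = (0.50/0.50)/(0.38/0.62) = 1.63.
- p = 50%: 0.15 + 0.14 = 29% v 0.25 + 0.10 = 35%. Odds ratio = (0.35/0.65)/(0.29/0.71) = 1.32.

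The true odds ratio is 1 in both. These are unadjusted values.

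**4. Simulation of the adjusted model.** The planned model is taken as dose group (two categories) plus six covariates with one linear term each. Baseline disease depends on a score of those covariates, set so that they carry 0%, 50% or 100% of the baseline difference between dose groups. Two-sided Wald test at 5%, 4,000 runs (standard error about 0.3 points at 5%, 0.7 at 22%).

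| Baseline, <20 v >20 Gy | Persistence | Carried by covariates | False positives, planned model | Median odds ratio (truth 1) |
|---|---|---|---|---|
| 30% v 50% | 50% | none | 9.0% | 1.37 |
| 30% v 50% | 50% | half | 6.1% | 1.17 |
| 30% v 50% | 50% | all | 4.5% | 1.01 |
| 30% v 50% | 80% | none | 23.0% | 1.75 |
| 30% v 50% | 80% | half | 9.2% | 1.31 |
| 30% v 50% | 80% | all | 5.2% | 1.00 |
| 50% v 30% | 80% | half | 10.3% | 0.75 |

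Repeat runs gave 5.0-6.1% for 50% persistence with half carried, 8.1-9.2% for 80% with half carried, and 23.0-23.6% for 80% with none carried. At 30% v 50%, a baseline case term brings the rate to 4.6-6.0% throughout. A smaller imbalance, 30% v 40% with half carried, gives 5.9% at 80% persistence and 4.8% at 50% without the term.

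**5. Balanced baseline (40% in both groups).** At 80% persistence the false-positive rate is 5.1% without and 5.0% with the term. Power for new cases of 15% v 45% goes from 42.8% to 48.3% at 80% persistence and from 42.2% to 42.5% at 50%. The gain depends on the set-up. With dose and baseline as the only predictors, 15% new disease and an odds ratio of 3 in cases and non-cases alike, power goes from 38% to 53% at 80% persistence and from 57% to 64% at 50%. That version leaves out the planned covariates.

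**6. Is case yes/no enough?** Suppose severe disease is 30% v 60% of baseline cases and persists in 90%, mild in 50%. Persistence among cases is then 0.3 x 0.9 + 0.7 x 0.5 = 62% v 0.6 x 0.9 + 0.4 x 0.5 = 74%, a difference that case status cannot see. At 30% v 50% with half carried, the false-positive rate is 13.4% as planned, 8.1% with case yes/no and 6.2% with extent. At a balanced 40% it is 7.6%, 10.1% and 6.6%.

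**The case against.** The design intends patients to start clean, so omitting a baseline term is consistent with that intent. For baseline disease to be the same disease at 24 months, it must outlast extraction, non-surgical treatment and the further treatment that consultants oversee after radiotherapy. This makes 80% persistence a high assumption. At 50% persistence with half the imbalance carried, little is left but a small bias in the odds ratio. No rate used here comes from the documents, and they offer no mechanism by which baseline disease would differ by parotid dose beyond the listed confounders. The simulated model also settles points that the plan leaves open: the dose coding in the logistic model and the form of the covariates. All of this stands, and it limits the size of the point. It does not remove the omission, because clearance is not verified.

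Three stronger readings are tempting, and the documents do not support them.

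- A reader might infer that surviving and recurrent disease can never be told apart. The charting at 6 and 12 months says otherwise: a baseline case who is a non-case at either visit and a case at 24 months is identifiable as recurrent. Only patients who are cases at every visit cannot be classed.
- A reader might take 23% as the expected false-positive rate. It needs a 20-point imbalance, 80% persistence and covariates that carry none of the imbalance, all together.
- A reader might say that the plan adjusts its secondary outcomes for baseline and breaks its own rule here. The baseline terms are stated for continuous secondary outcomes; dichotomous ones follow the logistic approach without one.

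**Conclusion.** The point holds as an improvement worth making, not as a demonstrated bias. The omission and the availability of the baseline chart are plain in the text, and some disease present before radiotherapy may be counted as outcome. Bias in either direction follows only if baseline disease differs by dose group beyond the listed confounders and persists, which the documents neither show nor exclude.

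On the assumed rates (30 v 120, no dose effect, 20% new cases, baseline 30% v 50%), the planned model's false-positive rate is about 5-6%, with an odds ratio of about 1.2, at 50% persistence and half the imbalance carried. It is about 8-9%, odds ratio about 1.3, at 80% with half carried. About 23% is the extreme. With a baseline term the rate is about 5-6%. If baseline is balanced there is no inflation, and in the set-up with the planned covariates the term adds at most a modest power gain, about 43% to 48%. A yes/no term is not a full fix if severity differs by dose.

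**What to change.** Add baseline periodontal status to the adjusted logistic model for periodontal disease and to the parallel models for dental dose and tumour location. Prefer extent, for example the number of sites with pockets of 4 mm or more, to case yes/no. Where extraction records allow, derive it from the teeth that remain after pre-radiotherapy extractions.

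Show 24-month disease separately for baseline cases and baseline non-cases. Among baseline cases, use the 6- and 12-month charts to identify recurrence, and state that patients who are cases at every visit cannot be classed as surviving or recurrent.

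The cost is a sentence or two in the analysis section, one model term, and some derivation work for the extent measure. No extra visits, measurements or patients are needed.

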### Exclusion criteria:

- Patients deemed to have poor prognosis, or patients to receive palliative treatment only (as advised by the Clinical Oncology team).
- Patients with less than 6 teeth before the radiotherapy start date.
- Patients with recurrent head and neck cancer, or patients receiving a repeat course of head and neck radiotherapy.
- Patients with diseases affecting tooth development (e.g. amelogenesis or dentinogenesis imperfecta) or salivary gland function (e.g. Sjogren's Syndrome).
- Patients with pre-existing trismus (mouth opening less than 35mm).

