### Diet advice

- Sugary and acidic food/drink to be consumed at mealtimes only
- Rinse mouth with 0.05% fluoride mouthwash after each sugar attack
- Advice on the use of sugar-free medications

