## **Sample size**

Sample size calculations were conducted based upon an independent samples t-test and correlation coefficient. Assuming the standard deviation of the number of carious teeth in post-radiotherapy head and neck cancer patients is 4.0 (based upon the results of a 10-year School of Dentistry audit conducted by the applicant fellow) and comparing patients receiving over 20 Gray to the 'spared' parotid gland with those receiving under 20 Gray (based upon a 80%/20% distribution seen in the Cancer Centre radiation dose audit), we would require a total sample of 150 patients with available data to have over 80% power to detect a difference of 3.0 in the mean number of carious teeth between the under 20 Gy and over 20 Gy groups as statistically significant at the 5% level. Furthermore a sample size of 150 patients would allow 80% power to detect, as significant at the 5% level, a correlation coefficient of 0.22 for the association between radiation dose to the 'spared' parotid gland (Gy) and the number of carious teeth. Assuming 30% dropout we would therefore need to recruit 215 patients.

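### The adjusted caries model leaves out smoking and medical history, which the periodontal model for the same exposure includes, and no reason is given

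*Combined protocol and SAP*

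**What the plan says.** Statistical analysis, item (1), specifies a multiple linear regression for number of carious teeth with "radiation dose to the 'spared' parotid gland as an explanatory variable", in categories, "along with potential confounding variables: dental radiation dose, oral hygiene practice, diet, and mouth opening". Smoking and medical history are not in that list.

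Item (1) then adds a second caries model: "Without categorising radiation dose, a separate analysis will be conducted using linear regression". It gives the increase in carious teeth per 10 Gy. Dose is its only named explanatory variable.

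Item (2) specifies a logistic regression for periodontal disease with "radiation dose to the 'spared' parotid gland as the explanatory variable and dental radiation dose", followed by "oral hygiene practice, diet, smoking, medical history, and mouth opening as potential confounders".

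Neither item explains the difference between the lists, and no other section adds the two variables to the caries model. The Sample size section is based on caries alone. Its target is "to detect a difference of 3.0 in the mean number of carious teeth", using a t-test with SD 4.0 and an 80%/20% split at 20 Gy, supplemented by a correlation of 0.22.

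**The concern.** This is a cohort study in which dose follows from clinical radiotherapy planning, so covariate adjustment is the main protection against confounding. A confounder has to be related to both the exposure and the outcome. The relation to exposure is the same whichever outcome is analysed, because both models use 'spared' parotid dose in the same patients. Once the plan names smoking and medical history as potential confounders in the periodontal model, it has accepted a possible relation to dose. The only open question for the caries model is whether either variable also affects caries, and the plan does not say that it does not.

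If either variable does affect caries, the adjusted caries estimate would carry part of that effect as though it were an effect of dose. The continuous-dose model is more exposed, since as written it adjusts for nothing.

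**Working it through.** **1. The covariate lists side by side** (Statistical analysis, items (1) and (2))

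| Term | Caries, dose in categories | Caries, per 10 Gy | Periodontal disease |
|---|---|---|---|
| 'Spared' parotid dose | yes | yes | yes |
| Dose to the teeth | yes | not named | yes |
| Oral hygiene | yes | not named | yes |
| Diet | yes | not named | yes |
| Mouth opening | yes | not named | yes |
| Smoking | not named | not named | yes |
| Medical history | not named | not named | yes |

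The counts are four, none and six covariates. The caries list is the periodontal list without smoking and medical history.

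**2. Whether the bias can be sized.** In a linear model, bias in the dose effect = γ × δ. Here γ is the effect of the omitted variable on the number of carious teeth, given dose and the four covariates. δ is the difference in the omitted variable between dose groups after adjustment for the same four covariates. The documents give neither quantity, nor the sign of either, so no estimate follows.

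**3. What the fix costs.** Inputs from the Sample size section: 150 evaluable patients split 80%/20%, so 120 and 30; difference 3.0; SD 4.0; 5% level (sidedness is not stated; two-sided assumed); 30% dropout.

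The plan's own figures first:
- Standard error = 4.0 × √(1/30 + 1/120) = 0.82 teeth.
- Power = Φ(3.0/0.8165 − 1.96) = Φ(1.71) = 95.7% (95.5% with the noncentral t). The stated figure of over 80% holds.
- Recruitment = 150/0.70 = 214.3, rounded up to 215, as stated.

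Let R² be the share of dose-group variance explained by the two added covariates (an assumption; the documents give no value). The standard error grows by 1/√(1 − R²), with the residual SD held at 4.0 although added covariates might reduce it:

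| R² | Power for 3.0 teeth, N = 150 |
|---|---|
| 0 | Φ(3.674 − 1.96) = 95.7% |
| 0.05 | Φ(3.581 − 1.96) = 94.8% |
| 0.10 | Φ(3.486 − 1.96) = 93.6% |
| 0.20 | Φ(3.286 − 1.96) = 90.8% |

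For the continuous-dose analysis, treat 0.22 as a partial correlation (an assumption). With k covariates, power = Φ(atanh(0.22) × √(150 − 3 − k) − 1.96):
- k = 0: 77.4%
- k = 4: 76.3%
- k = 6: 75.7%

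Moving from no covariates to six costs 1.7 percentage points, of which the last two covariates cost 0.6. The 77.4% at k = 0 is itself a little under the stated 80% on a two-sided test. That is a separate matter and is not caused by the covariates.

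**4. Whether the variables will exist.** The periodontal model cannot be fitted as written without smoking and medical history. Yet neither is named as a study data field in the Clinical assessment, Clinical data transfer and storage, or Spreadsheets sections. Medical history appears as a consideration for extractions, and smoking appears as something to avoid before saliva collection. One or both may come from the questionnaires, but the documents do not show this.

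**The case against.** The strongest reply is that different outcomes can properly have different confounder sets. A variable related to dose but not to caries need not be in the caries model, so a difference between the lists is not in itself an error. This stands as a principle, but the plan does not invoke it. If the difference is deliberate, it needs a stated reason.

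The protocol's own support for a link to caries is also thin. The diet section includes "Advice on the use of sugar-free medications", but that concerns sugar intake, and diet is already in the caries model. Diseases affecting salivary gland function are excluded, which removes that part of medical history by design. Nothing in the documents links smoking to caries. These objections limit the point to possible confounding. They do not remove it, because the plan neither argues nor shows that the two variables are irrelevant to caries.

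A reader might infer three stronger things that the documents do not support:

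- **A sizeable bias.** Assuming an effect of 1 to 2 teeth and an imbalance of 10 to 30 percentage points gives 1 × 0.10 = 0.1 to 2 × 0.30 = 0.6 teeth, or 3% to 20% of the 3.0-tooth difference. Both inputs are invented, and a crude imbalance is not the δ needed for a model already adjusted for four covariates. Even at face value, the whole range lies below one standard error (0.82).
- **Primary results that cannot be compared because the lists differ.** One result is a mean difference in tooth count and the other an odds ratio. The same covariates would not put them on a common scale.
- **A threat to the sample size.** The study is sized on caries, but through an unadjusted t-test and a correlation, not through the adjusted regression at issue here.

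**Conclusion.** The point holds in a limited form. The adjusted caries model omits two variables that the plan itself treats as potential confounders of the same exposure in the same patients, without a reason, and the continuous-dose caries model names no covariates at all. The consequence is potential residual confounding in the caries estimates, of unknown size and direction. It is a minor point, worth acting on because the remedy is cheap and specific.

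The conclusion rests on two things: that a variable's relation to dose does not depend on which outcome is analysed, and that smoking and medical history will be collected, as the periodontal model requires. The cost figures rest on the assumed R² values, a two-sided 5% test and the plan's own SD and group split.

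**What to change.** In Statistical analysis, item (1), add baseline smoking and baseline medical history to the adjusted caries regression, using the same variables and coding as in item (2). Report the per-10-Gy caries regression with that same covariate set. If the investigators prefer to keep a shorter list for caries, they should state why.

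In the same edit, say where smoking and medical history are recorded and how they are coded, since the periodontal model needs this in any case.

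The cost is a change of wording and a few degrees of freedom out of about 150; the exact number depends on how medical history is coded. The 150 evaluable and 215 recruited patients need not change. If it turns out that either variable is not being captured, collecting it is an added cost, but one that the periodontal model already imposes.

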#### **SPECIAL CASES**

Dental phobic patients – may consider additional extraction of any tooth with caries.

Impacted/unerupted teeth – extract when in communication with oral cavity, carious, or other pathology suspected (e.g. cyst formation, resorption of adjacent teeth).

Retained roots/apices – leave when no pathology and encased entirely within bone.

Patients deemed to have poor prognosis or to receive palliative treatment only – may limit number of extractions on this basis.

Dental neglect (toothbrushing <1x per day, intake of >5 sugar attacks per day, caries affecting >75% of remaining teeth) – may consider additional extraction of teeth or complete dental clearance.

Patients with oral cancer – additional teeth in close proximity to tumour may require removal as part of the oncology surgical approach.

Patients taking bisphosphonate medications – need to liaise with Oral Surgery or Maxillofacial Team.

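### The caries models never account for how many teeth were at risk, so the dental-dose estimate, and less so the per-10-Gy parotid estimate, is biased if tooth number is related to dose

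*Combined protocol and SAP*

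**What the plan says.** All references are to the combined protocol and SAP.

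- **Entry and baseline.** Exclusion criteria sets a floor only: "Patients with less than 6 teeth before the radiotherapy start date". Study design has a "Pre-radiotherapy assessment at baseline and patients rendered dentally fit (i.e. free of dental disease", so caries found later can range from none up to the number of teeth kept.
- **Adjusted parotid model.** Statistical analysis (1): "Adjusted analysis will be performed using multiple linear regression, with the number of carious teeth as the outcome variable", with categorised spared-parotid dose "along with potential confounding variables: dental radiation dose, oral hygiene practice, diet, and mouth opening".
- **Per-10-Gy parotid model.** In the same section, "a separate analysis will be conducted using linear regression with the number of carious teeth as the outcome variable"; continuous parotid dose is the only explanatory variable named.
- **Other exposures.** "Similar analyses will be undertaken to determine the effects of dental radiation dose and tumour location on the number of carious teeth". Tooth dose is not a side question: the Clinical hypothesis names it beside parotid dose.
- **Tooth number.** It appears in no caries model. Tooth loss is listed only as a secondary outcome.
- **Extractions before radiotherapy.** Under Special cases, for patients with oral cancer, "additional teeth in close proximity to tumour may require removal as part of the oncology surgical approach". The Extractions table and the dental-neglect entry also allow removal because of caries.

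**The concern.** A patient with 6 teeth cannot have more than 6 carious teeth; a patient with 28 can. Tooth number is therefore likely to predict the raw count whatever the dose.

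Whether this matters depends on whether tooth number is also related to dose. The oral-cancer entry under Special cases offers a route: tumour site can determine which teeth are removed and, plausibly, how much dose the remaining teeth receive. If patients with higher tooth dose start with fewer teeth, a real dental-dose effect is diluted or may look protective. If they start with more, it is exaggerated. If there is no relation, the slope is unbiased and only a little precision is at stake.

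The two exposed analyses are dental dose, which is part of the primary hypothesis, and the per-10-Gy parotid regression, which names no covariates.

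**Working it through.** **1. The plan's own figures (Sample size; two-sided 5% assumed).**
- 3.0-tooth contrast, SD 4.0, 30 against 120 patients: SE = 4.0 × √(1/30 + 1/120) = 0.816; 3.0/0.816 = 3.67; power = Φ(3.67 − 1.96) = 96% (95% by noncentral t). This agrees with the stated figure of over 80%.
- Correlation 0.22, n = 150: 78% by the regression-slope t-test and 77% by Fisher z, close to the stated 80%.
- Dropout: 150/0.7 = 214.3, so 215.

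**2. Inputs for the bias check.** The documents give no tooth distribution and no dose–tooth correlation, so everything here is assumed except n = 150 and a count SD set near the plan's 4.0.
- Dental dose D is standard normal.
- Teeth = 17 − s·D + noise, total SD 5.5, rounded and held within 6–28.
- Carious teeth are binomial(teeth, p), with logit p = −1.6 + b·D + a normal patient effect of SD 1.3.
- This gives mean count 3.86, SD 3.92 and risk per tooth 0.227.
- s is the number of teeth fewer per SD of dental dose; s = 0.5, 1 and 2 correspond to dose–tooth correlations of about −0.09, −0.18 and −0.36 (s/5.5).

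**3. Hand check, no true effect (b = 0).** Spurious slope ≈ −s × 0.227, so about −0.23 at s = 1; simulated, −0.21 after rounding and limits. SE ≈ 3.92/√150 = 0.32. Shift = 0.21/0.32 = 0.66 SE. False positives ≈ Φ(−1.96 + 0.66) + Φ(−1.96 − 0.66) = 9.7% + 0.4% = 10%.

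**4. Simulation, dental dose alone.** Power is at b = 0.38, which gives r = 0.22 when s = 0. Ranges reflect simulation error.

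| Teeth fewer per SD of dose | False positives, raw | With tooth covariate, HC3 | Power, raw | Power, covariate |
|---|---|---|---|---|
| 0 | 5% | 4–5% | 78% | 81% |
| 0.5 | 6–7% | 5% | 67–68% | 81–82% |
| 1 | 10–11% | 5% | 54% | 80% |
| 2 | 26% | 5% | 28–29% | 76–78% |

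At s = 1 the raw slope under a real effect is 0.66 carious teeth per SD, against 0.89 without the link (0.66/0.89 = 74%). With 1 *more* tooth per SD, raw false positives are 11% and power is inflated to 92%. With parotid dose also in the model (dose correlation 0.3–0.7), s = 1 gives 8–10% false positives.

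**5. Parotid dose, teeth depending on dental dose only.**
- Per-10-Gy regression: 6–8% false positives at s = 1 and 7–15% at s = 2; 5% with the covariate.
- Adjusted model including dental dose: 5–6% without the covariate, because dental dose already closes the path.
- 20 Gy contrast: the shift is 0.11–0.53 carious teeth, so power = Φ((3.0 − 0.11)/0.816 − 1.96) = 94% down to Φ((3.0 − 0.53)/0.816 − 1.96) = 86% (85–94% simulated).

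**6. Precision when tooth number is unrelated to dose.** The covariate cuts the SE by about 4.5%, so the raw SE is about 5% larger (1/0.955 = 1.047). If caries-prone patients also have fewer teeth (assumed correlation −0.1, −0.2, −0.3), the cut shrinks to 2.6%, 1.1% and 0.1%.

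**7. Limit of the covariate.** In that caries-prone case, conditioning on tooth number itself ties dose to proneness. False positives with the covariate are then 5%, 7% and 9% at s = 1, and 7%, 12% and about 20% at s = 2, against 10–12% and 29–34% raw. A count model with a log(teeth) offset stays at 5–6%.

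Oral hygiene, diet and mouth opening were not simulated.

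**The case against.** The case against is substantial, and much of it stands.

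- **The dose–tooth link rests on one conditional sentence.** Special cases says teeth near an oral tumour may need removal, with no frequency and no mention of dose. The criteria in the Extractions table are dental. The sign is open too: removing the teeth nearest the tumour could lower the mean dose of those that remain. This stands, so the bias is conditional.
- **A reader might infer that false positives reach 26% or that power falls to 28%.** Those figures need a dose–tooth correlation near −0.36, which nothing in the documents supports.
- **A reader might infer a definite loss of precision.** It is at most about 5% of the SE and can vanish. The planned SD of 4.0 is for the raw count and so should already contain tooth-number variation. At 2 teeth per SD the covariate makes the SE 3–7% larger.
- **A reader might infer that the powered comparison is undermined.** It is not: the 3.0-tooth contrast keeps at least 85% power, and the adjusted parotid model stays at 5–6%. A direct link between tooth number and parotid dose would change that (9% at 1 tooth per SD), but no section documents one.
- **A reader might infer inconsistency with the baseline-adjusted secondary outcomes.** The comparison is weak: those models adjust for the outcome's own baseline, and baseline caries is about zero by design.

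What does not stand is that the listed covariates deal with the problem. Oral hygiene, diet and mouth opening do not measure teeth at risk, and the per-10-Gy model names none of them.

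**Conclusion.** The omission is plain in the text, and nothing elsewhere in the document repairs it. It biases the dental-dose estimate, and to a lesser degree the unadjusted per-10-Gy parotid estimate, if tooth number at the start of radiotherapy is related to dose. That relation is plausible for oral tumours, but its size and direction are unknown. For a modest link of 0.5 to 1 fewer teeth per SD of dental dose, false positives are 6–11% and power at r = 0.22 falls from about 78% to 68–54%. With no link there is no bias and the SE is 0–5% larger. These figures rest on the assumed tooth distribution and per-tooth risk: at 1 tooth per SD, a tooth SD of 4 gives 11% false positives and a 15% risk per tooth gives 8%. The documents do not support extending the point to the sample size, the 3.0-tooth contrast or the adjusted parotid model. The change is worth making because it is nearly free and protects an exposure named in the primary hypothesis.

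**What to change.** - **Main change.** In the dental-dose and per-10-Gy parotid caries models and, for consistency, the categorised parotid model, add the number of teeth present at the start of radiotherapy as a covariate, with HC3 robust errors. This keeps results on the tooth-difference scale of the hypothesis and sample size.
- **Source.** No visit charts teeth at the start of radiotherapy, so derive the number from the baseline charting less extractions done before radiotherapy ("Dental treatment required pre-radiotherapy (e.g. restorations and extractions) will be co-ordinated by the School of Dentistry"), or count the teeth contoured on the planning CT. It need not be perfect: an error of SD 1–2 teeth still gives 5–6% false positives.
- **Not teeth at 24 months.** Later tooth loss can itself result from caries and dose.
- **Alongside.** Because caries-driven extractions may leave caries-prone patients with fewer teeth, report a count model with a log(teeth) offset and robust errors.
- **Tumour location.** Report results with and without the tooth count. Removal can follow from location, so the adjusted result answers a conditional question. With 1, 2 or 3 teeth removed and equal risk per tooth, the raw difference is −0.2, −0.4 or −0.7 carious teeth, and about 0 after adjustment.

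**Cost:** one derived variable and slightly more analysis, with no new visit or measurement.
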